Secondary Objective #3: To assess the duration of antibody responses to Na-GST-1 induced by vaccination with Na-GST-1/Alhydrogel® delivered with or without AP 10-701 or CpG 10104.

*Secondary Outcome #2 and #3 Measures:*

The following parameters will be evaluated for each formulation of Na-GST-1, in comparison to the saline placebo control:

1. The anti-Na-GST-1 IgG antibody response, by a qualified indirect enzyme-linked immunosorbent assay (ELISA) at approximately 14 days after each vaccination, and approximately 1, 2, 4, 6, 7, 8 and 10 months after the third dose.

*Analysis Plan:*

- a. The proportion of participants with detectable anti-Na-GST-1 IgG responses will be summarized as a descriptive measure.
- b. IgG levels will be displayed graphically by study group using notched box plots at each time point.
- c. Geometric mean antibody responses will be compared between vaccine formulation groups at each time point. Comparisons between groups will be made by a one-way analysis of variance (ANOVA) with pair-wise comparisons between groups made by contrasts.
- d. Geometric mean antibody responses for each antigen will be compared using a regression model with main effects for the doses of Na-GST-1 (0 or 100µg), AP 10-701 (0 or 5 µg), and CpG 10104 (0 or 500µg).
- e. For antigen-specific log IgG levels, a three-way ANOVA will be conducted, with Na-GST-1, CpG 10104 and AP 10-701 doses as factors.
- f. Pair-wise comparisons of IgG levels on study Day 126 (2 weeks after the third vaccination) across all combinations of Na-GST-1 doses (i.e., 0 [placebo] or 100 µg), AP 10-701 doses (i.e., 0 or 5 µg), and CpG 10104 doses (0 or 500µg) will be assessed using Tukey's HSD.
- g. Percent change in IgG antibody levels from days of vaccination to days 7, 14 and 28 post-vaccination will be compared between vaccine formulation and dose groups. Values will be reported with 95% confidence intervals.
- h. Percent change in IgG antibody levels from vaccination day #1 to #2, from vaccination day #2 to #3, and from vaccination day #3 to day of CHHI will be compared between vaccine formulation and dose groups to assess the sustainability of the response from trough to trough and post-CHHI. Values will be reported with 95% confidence intervals.
- i. Percent change in IgG antibody levels from the peak following the third vaccination, to 1, 2, 4, 6, 7, 8 and 10 after the third vaccination. Values will be reported with 95% confidence intervals.

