## 5. STATISTICAL METHODOLOGY

### 5.1 General Considerations

The statistical analyses will be performed by Quartesian Clinical Research, using SAS Version 9.3 (or higher). All tables, figures and listings will be produced in landscape format. In general, all data will be listed by the subject and visit/time point where appropriate.

Data will be summarized by time-point where appropriate. The total number of subjects in the study group (N) under the stated population will be displayed in the header of summary tables.

Data will be summarized using descriptive statistics for continuous variables. Unless otherwise stated, descriptive statistics will include number of subjects, mean, standard deviation, minimum, median and maximum for all endpoints in case of  $n < 2$ , where n indicates the number of evaluable subjects at the particular time point, only n, mean, minimum and maximum will be displayed. The statistic "Missing" will also be evaluated by enumerating the number of missing entries/subjects, if any at that visit, and presented along with summary statistic. Display NC if any value is not computable.

Decimal Precision Convention: The minimum and maximum statistics will be presented to the same number of decimal places as the original data. The mean and median will be presented to one more decimal place than the original data, whereas the standard deviation will be presented to two more decimal places than the original data.

For categorical variables, counts and percentages will be used. The count [n] indicates the actual number of subjects with non-missing value at particular visit or actual number of subjects with that event or category, which should always be less than or equal to the total number of subjects in the respective study group [N]. Percentage will be obtained by:  $\% = (n/N) * 100$ .

Unless otherwise stated, all percentages will be expressed to one decimal place.

Also, the distributions for continuous variables will be examined for normality using Shapiro-Wilk tests. If any deviation in the normality assumption is judged, then the data will be analyzed using appropriate non-parametric tests.

The following conventions will be applied to analyses/data presentation:

All dates will be displayed in DDMMYY format.

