#### 5.7.4.2 Secondary Endpoint Analysis

Fecal egg counts of the subjects in each of the vaccination (Groups 1, 2 and 3) and placebo (Group 4) groups will be assessed for normality. If normality assumption is confirmed, the comparison between vaccination groups (Group 1, 2 and 3) and placebo group (Group 4) will be done using T-test. Otherwise, the vaccination groups (Group 1, 2 and 3) will be compared with the placebo group (Group 4) using a Wilcoxon-Mann-Whitney rank-sum test. Continuous data will be summarized using the descriptive statistics (mean, median, minimum, maximum and median 95% CI). Mean or Median differences and corresponding 95% CIs will be computed for each pairwise comparison.

Time to patent infection (i.e., the first timepoint at which hookworm eggs are detectable in a fecal sample) will be displayed using Kaplan-Meier estimates, with log-rank tests used to compare the distribution of time-to-patency between groups and censoring of early withdrawals or those failing to develop patent infection.

The detectable anti-*Na-GST-1* IgG responses will be summarized as a descriptive measure using descriptive statistics (mean, standard deviation, median, minimum and maximum) for each observed measurement by vaccination groups and placebo. IgG levels will be displayed graphically by study group using time series and notched box plots at each time points.

Geometric mean antibody responses will be compared between vaccination groups and placebo at each time point using an ANOVA model. An ANOVA model will be fitted with IgG responses as the dependent variable and vaccination groups and placebo as independent variables. The estimated geometric least square means and geometric least square means difference from the model, 2-sided *p*-value and 95% CI for vaccination groups compared to placebo group will be constructed and presented for each time point.

Percent change in IgG antibody levels from days of vaccination to days 7, 14 and 28 post-vaccination, as well as percent change in IgG antibody levels from the peak following the third vaccination to 1, 2, 4, 6, 7, 8, and 10 months post-vaccination will be summarized using descriptive statistics (mean, standard deviation, median, minimum, maximum and 95% CI) for each observed measurement along with the percent change from baseline.

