A longitudinal model will be built to describe the IgG levels over time. Using a longitudinal panel model, differences in antibody isotype levels by vaccination groups and placebo will be explored. The analysis will take account of the correlation between measurements on the same subject. A mixed model repeated measure (MMRM) will be fitted with IgG levels as the dependent variable and vaccination groups and placebo, visits and interaction between groups and visits as independent variables. the estimated geometric means Standard Error and geometric means difference from the model, 2-sided *p*-value and 95% CI for vaccination groups and placebo will be constructed.

Logistic regression will be explored for the binary response of hookworm infection post-CHHI as a function of antibody response. Dependant variable will be the hookworm infection status (Positive/Negative) and independent variable will be the IgG responses and vaccination groups and placebo. Estimated number of subjects, Standard Error and odds ratio from the model, 2-sided *p*-value and Wald 95% CI for vaccination groups and placebo will be constructed.

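### SAP 5.7.4.2 omits the protocol's proportion with detectable IgG without declaring it, words the replacement table as detectable-only, and adds a percent change from a baseline that may lie at the assay floor

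*SAP*

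**What the plan says.** Item (a) of the protocol's analysis plan for Secondary Outcomes 2 and 3 (Section 11.4) is a responder measure: "The proportion of participants with detectable anti-Na-GST-1 IgG responses will be summarized as a descriptive measure".

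The corresponding sentence in SAP 5.7.4.2 reads "The detectable anti-*Na-GST-1* IgG responses will be summarized as a descriptive measure using descriptive statistics", followed by a list (mean, standard deviation, median, minimum, maximum) for each measurement by group. The SAP text gives no proportion with detectable IgG. SAP Section 7 declares one change from the protocol, concerning item (e), the three-way ANOVA.

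The other IgG analyses in SAP 5.7.4.2 carry no such qualifier:
- plots: "IgG levels will be displayed graphically by study group using time series and notched box plots at each time points";
- a geometric-mean ANOVA at each visit: "An ANOVA model will be fitted with IgG responses as the dependent variable and vaccination groups and placebo as independent variables", with "2-sided *p*-value and 95% CI for vaccination groups compared to placebo group will be constructed and presented for each time point";
- a longitudinal model: "A mixed model repeated measure (MMRM) will be fitted with IgG levels as the dependent variable";
- a logistic regression of infection status on IgG and group.

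On change over time, the protocol already plans percent changes (items g to j). The SAP repeats some of these and adds a summary "for each observed measurement along with the percent change from baseline". SAP 5.2 defines baseline as the last value before the first dose. Where a value cannot be calculated, SAP 5.1 says "Display NC if any value is not computable".

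Neither document defines detectable, gives an assay limit or Day 0 level, or says how a value below the limit enters a geometric mean. The missing-data rules in SAP 5.1 cover partial dates only.

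**The concern.** A protocol-specified summary has gone without being declared. What replaces it, if programmed as worded, averages only subjects who responded. Failure to respond is one of the differences an added immunostimulant might make, and the second study hypothesis in both documents is that the TLR agonists raise IgG above Alhydrogel alone. The contrasts named for the SAP's ANOVA are against placebo, so a reader comparing formulations will look at the descriptive table.

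The added percent change from baseline has a separate weakness. The subjects are hookworm-naive and have not received this vaccine (exclusion criteria 26 and 28), so Day 0 values may well sit at or near the assay floor. An arithmetic mean of percentages is then driven by small or arbitrary denominators, or cannot be computed at all.

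**Working it through.** The documents state no power, effect size, assay limit or responder rate for IgG, so there is no figure of the plan's own to reproduce. Every AU value below is an assumption for illustration. Only the group size of 12 comes from the documents.

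**Text side by side.** Protocol item (a) has a count over participants as its numerator and all participants as its denominator. The SAP sentence has no denominator, and its subject is the set of detectable responses. These are different quantities, and the second does not contain the first.

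**What a detectable-only table shows.** Formulation A has 12/12 subjects at 100 AU. Formulation B has 4/12 at 100 AU and 8/12 undetectable.
- Mean of detectable values: 100 AU for A and 100 AU for B.
- Proportion detectable: 12/12 = 100% and 4/12 = 33%.
- Mean over all subjects, counting undetectable as 0: 100 AU and (4 × 100 + 8 × 0)/12 = 33.3 AU.

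**The same with spread.** Responders are log-normal with geometric mean 100 AU and geometric SD 2.5. The strong group has 12/12 responders and the weak group 6/12, with non-responders set to half the limit. There were 4,000 simulated data sets per setting, with t-tests on the log scale.
- Detectable values only: strong/weak ratio about 1.0, with p<0.05 in about 5% of data sets, which is the chance rate.
- All subjects kept: the expected ratio is (100/floor)^(6/12). A limit of 2 AU gives a floor of 1 and √100 = 10.0. A limit of 20 AU gives a floor of 10 and √10 = 3.2. The simulation agrees, with p<0.05 in 96% and 68% of data sets respectively.
- Responder proportion, two-sided Fisher test, 12/12 against 6/12: 2 × C(12,6)/C(24,6) = 2 × 924/134,596 = 0.014. With 3/12 in the weak group p = 0.0003, and with 9/12 p = 0.22. At 12 per group the proportion therefore reveals large shortfalls, not small ones.

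**Percent change from a small reference.** The formula is 100 × (post − base)/base.

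| Base (AU) | Post (AU) | Percent change |
|---|---|---|
| 5 | 100 | 1,900% |
| 1 | 100 | 9,900% |
| 0.5 | 100 | 19,900% |
| 0.1 | 100 | 99,900% |
| 0.5 | 20 | 3,900% |
| 0 | any | not computable |

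A rise to only 20 AU from 0.5 AU (3,900%) exceeds a rise to 100 AU from 5 AU (1,900%). Take two subjects who both reach 100 AU, from 0.5 and 5 AU. Their arithmetic mean percent change is (19,900 + 1,900)/2 = 10,900%, almost all of it from one subject. Their fold-rises are 200 and 20, with geometric mean √(200 × 20) = 63.

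**The case against.** A reader might infer that the SAP analyses only detectable IgG, so that non-responders disappear and a weak formulation can pass for a strong one across the immunogenicity results. The documents do not support that. The plots, ANOVA, mixed model and logistic regression are written on IgG levels or responses without restriction, and SAP 5.1 lists data by subject and visit. Non-responders would leave the models only if undetectable values were coded as missing, or as zero before taking logs. The SAP leaves that open but does not plan it.

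Four further points deserve weight.
- The SAP sentence may be a loose paraphrase of item (a). It covers placebo too, and a truly detectable-only table could leave that column nearly empty. This is plausible, but a programmer works from the text.
- SAP 5.1 normally shows the number of subjects, a missing count and the group total, so formulation B would probably appear as n = 4 under N = 12. This softens the illustration. However, the list in 5.7.4.2 omits n, and a missing count does not separate undetectable from not sampled. The table shells are in a separate document that cannot be seen here.
- Percent change is the protocol's own choice. Changes from vaccination 2, vaccination 3 or the post-dose-3 peak do not use Day 0. The protocol's changes from the first vaccination day do, so the SAP's explicit addition extends a weakness already there.
- Percent change equals 100 × (fold-rise − 1), so fold-rise from Day 0 still depends on the floor. This stands. The gain is that a geometric mean is not dominated by the smallest denominators.

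**Conclusion.** The point holds for one table and one change measure. The omission of the responder proportion and its absence from SAP Section 7 are matters of text and need no assumption. That the replacement table hides failure to respond depends on reading its wording literally. On that reading it cannot separate 12/12 from 4/12 or 6/12 responders at the same level (ratio about 1.0), while all-subject geometric means differ 3.2- to 10.0-fold in the 6/12 example, over assumed limits of 20 to 2 AU. No responder rate in the documents says such a gap will occur, and Protocol 2.2.1 reports that all three formulations induce specific IgG.

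The instability of percent change rests on Day 0 values at or near the floor. That is plausible in this population but not stated.

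IgG is a secondary outcome, and neither the primary infection endpoint nor the sample size is touched. The correction is worth making because it is cheap and because, with 12 per group, a few non-responders matter.

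**What to change.** Amend SAP 5.7.4.2 before unblinding:
1. For each group and time point, report the number and proportion of all sampled subjects with detectable IgG, with an exact 95% CI, and state the threshold that defines detectable.
2. Compute descriptive statistics and geometric means over all sampled subjects under one pre-stated convention for values below the limit (for example half the limit), with a sensitivity check on that choice. Apply the same convention in the ANOVA and mixed model.
3. Report change from Day 0 as geometric mean fold-rise with 95% CI. Keep percent change for references that are detectable, such as the post-dose-3 peak.
4. List any remaining departure from Protocol 11.4 in SAP Section 7.

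The cost is SAP wording and programming, with no new samples or visits. The laboratory must supply the assay limit, which the documents do not give. One limitation remains: fold-rise from Day 0 still depends on the below-limit convention, which is why the convention and its sensitivity check must be written down.

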### Study Day 7 (Visit #3)

1. Perform basic history and physical exam (including injection site), emphasizing examination of any acute complaints.
2. Record vital signs (oral temperature, pulse, and blood pressure).
3. Review and collect subject post vaccination symptom memory aid.
4. Obtain blood for cell-mediated immunity (CMI) assays.

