#### Study Hypotheses:

This study is not designed to test statistically significant small differences in efficacy between different adjuvant formulations of the *Na-GST-1* hookworm vaccine as assessed in the CHHI model. Rather, it is intended to provide an indication of an impact on infection as assessed by CHHI, and to detect large differences in efficacy with acceptable power. Furthermore, the study intends to assess the safety, reactogenicity, and immunogenicity of three novel adjuvant formulations of *Na-GST-1*: *Na-GST-1*

formulated on Alhydrogel, *Na*-GST-1/Alhydrogel® administered with AP 10-701, and *Na*-GST-1/Alhydrogel® administered with CpG 10104.

The chosen sample size principally facilitates the assessment of efficacy (as estimated by infection status following CHHI) as well as safety, as discussed in SAP Section 3.1, Sample Size Considerations. Given that, this study will attempt to assess the following hypotheses:

1. Administration of the *Na*-GST-1/Alhydrogel® vaccine with either AP 10-701 or CpG 10104 will result in a reduced proportion of subjects infected with hookworm following CHHI compared to placebo controls.
2. Co-administration of *Na*-GST-1/Alhydrogel® vaccine with either AP 10-701 or CpG 10104 will increase the IgG antibody response to *Na*-GST-1 compared to when *Na*-GST-1/Alhydrogel® is administered alone.
3. Co-administration of *Na*-GST-1/Alhydrogel® vaccine with either AP 10-701 or CpG 10104 will increase the affinity of induced IgG antibodies to *Na*-GST-1 compared to when *Na*-GST-1/Alhydrogel® is administered alone.
4. Co-administration of the *Na*-GST-1/Alhydrogel® vaccine with either AP 10-701 or CpG 10104 will increase the induction of specific MBCs to *Na*-GST-1 compared to when *Na*-GST-1/Alhydrogel® is administered alone.
5. Co-administration of the *Na*-GST-1/Alhydrogel® vaccine with either AP 10-701 or CpG 10104 increases the neutralizing capacity of induced IgG antibodies to *Na*-GST-1 compared to when *Na*-GST-1/Alhydrogel® is administered alone.
6. Co-administration of *Na*-GST-1/Alhydrogel® vaccine with either AP 10-701 or CpG 10104 will increase the avidity of induced IgG antibodies to *Na*-GST-1 compared to when *Na*-GST-1/Alhydrogel® is administered alone.

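### The SAP specifies no IgG contrast of the CpG or AP arms against Alhydrogel alone, although its hypothesis 2 is that comparison, and it does not declare that the protocol's contrasts were left out.

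*SAP*

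**What the plan says.** **Hypothesis.** SAP 5.1 (Study Hypotheses, no. 2) and Protocol 11.1 both state that giving Na-GST-1/Alhydrogel "with either AP 10-701 or CpG 10104 will increase the IgG antibody response to" the antigen, relative to the same vaccine without an immunostimulant. The comparator is Group 1, not saline.

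**SAP models.** In SAP 5.7.4.2 the per-visit model is described as follows: "An ANOVA model will be fitted with IgG responses as the dependent variable". Its output is "The estimated geometric least square means and geometric least square means difference from the model", with a two-sided p-value and "95% CI for vaccination groups compared to placebo group will be constructed and presented for each time point". The MMRM in the same section takes IgG levels as the response. It promises a geometric mean difference, p-value and interval for the vaccination groups and placebo, without saying which group is compared with which.

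**Protocol.** Section 11.4, under secondary outcomes 2 and 3, lists:
- item c: "Comparisons between groups will be made by a one-way analysis of variance (ANOVA) with pair-wise comparisons between groups made by contrasts";
- item d: a regression with main effects for antigen, AP 10-701 and CpG 10104;
- item e: a three-way ANOVA on log IgG;
- item f: Tukey pairwise comparisons at Day 126.

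**Declared changes.** SAP Section 7 mentions item e only, as conditionally not required.

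**Change summaries.** The SAP also plans "Percent change in IgG antibody levels from days of vaccination to days 7, 14 and 28 post-vaccination", taken over from protocol item g.

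**The concern.** A programmer working from SAP 5.7.4.2 would produce three vaccine-versus-saline comparisons per visit and nothing that sets CpG or AP against Alhydrogel alone. Protocol 11.4 opens by giving comparison of immune-response patterns between formulations as part of the trial's purpose, and Protocol 2.2.1 wants formulations compared so that the most promising can be selected. If the between-formulation contrast is chosen only after unblinding, its time point, scale, variance and multiplicity rule will all be chosen with the data in view.

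The question is not settled beforehand for both immunostimulants. Protocol 2.1.6 reports a significant IgG gain for CpG over Alhydrogel alone, but gives no such result for AP 10-701.

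**Working it through.** **1. Comparisons side by side.** The documents give no IgG power or SD. The stated power figures concern the infection endpoint and do not bear on this point.

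| Item | Group 2 vs 1 and Group 3 vs 1 covered? |
|---|---|
| Hypothesis 2 | Yes, this is the hypothesis |
| Protocol item c, pairwise contrasts | Yes |
| Protocol item d, main effects | Yes (see below) |
| Protocol item f, Day 126 Tukey | Yes |
| SAP ANOVA | No, placebo only |
| SAP MMRM | Comparator not named |
| SAP Section 7 | Mentions item e; silent on the contrasts in c, and on d and f |

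Item d is the four-group ANOVA in other parameters. Every vaccine arm has the antigen and each immunostimulant appears in one arm. So the antigen coefficient is Group 1 − Group 4, the CpG coefficient is Group 2 − Group 1, and the AP coefficient is Group 3 − Group 1, with 48 − 4 = 44 error df either way. A numerical fit confirmed this. The missing contrasts therefore need no new model.

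**2. Can the saline comparisons substitute?** Assume Groups 1 and 2 are truly equal, both 1.5 log10 above saline, with log10 SD 0.3, 0.5 or 0.7 in every arm and 12 per arm. On the log scale both beat saline in 100%, 100% and 99.8% of simulated trials. Two significant results against saline are therefore compatible with no immunostimulant effect at all.

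**3. Does the scale matter?** In the same simulation on raw IgG, both arms beat saline in only 95%, 32% and 5% of trials, and the Group 2 vs 1 type I error is 7–9% instead of 5%. The transform should be written down.

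**4. Variance for the added contrast.** Let the three vaccine arms share variance σ² and let placebo sit at the assay floor with SD near 0. The pooled variance is then (11 + 11 + 11 + 0)σ²/44 = 0.75σ². The 44-df critical value of 2.015 acts as 2.015 × √0.75 = 1.745 on a 33-df t statistic, whose two-sided tail is 9.0%. Simulation with vaccine log10 SD 0.5 agrees:

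| Assumed placebo SD | Four-group pooled type I error |
|---|---|
| 0 | 9.0% |
| 0.1 | 8.8% |
| 0.2 | 8.2% |
| 0.5 (equal) | 5.0% |

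Using the vaccine arms alone (33 df) returns 5.0–5.1% throughout.

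**5. What the contrast could detect.** The standard error of a difference is SD × √(2/12). For a 3-fold rise, log10 3 = 0.477, so the noncentrality is 0.477/(SD × 0.408), or about 3.9, 2.3 and 1.7 for SD 0.3, 0.5 and 0.7. Two-sided 5% power from the noncentral t with 44 df is 97%, 63% and 37%; 33 df lowers each by less than one point. The fold rise detectable with 80% power is about 2.3, 3.9 and 6.6. The SDs are assumed.

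**6. Sampling days.** After doses 1, 2 and 3 the day-7 visits are Days 7, 63 and 119. At Day 7 the only blood instruction is "Obtain blood for cell-mediated immunity (CMI) assays", and Days 63 and 119 are the same. Appendix A agrees: 50 mL is drawn at each, which is the cellular volume without the 10 mL for antibody. Day 28 after doses 1 and 2 (Days 28 and 84) is a telephone call. Only Day 140, 28 days after dose 3, supplies a day-28 antibody sample.

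**The case against.** The strongest reply is that the protocol already plans these tests, SAP Section 1 says the SAP is to be read with the protocol, and Section 7 waives only item e. A reader might infer that hypothesis 2 is never tested anywhere. The documents do not support that, and this part of the reply stands. It does not cure the gap. The SAP presents itself as the explicit guidance for the final analyses, and it restates item c with placebo as the only comparator.

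There is also a version caution. The SAP cites protocol Version 4.0 of September 2019, the supplied protocol bears a 2025 IRB approval date, and their lists of secondary objectives differ. Some of the mismatch may reflect versions. The SAP's own hypothesis still lacks a specified test in the SAP's own methods.

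Other replies stand as limits on the point:
- Placebo is the prespecified comparator for the IgG outcome (Protocol 3.2.2, SAP 4.2), so making placebo descriptive only would be a new departure.
- A reader might take the models to use untransformed IgG. The SAP is silent on the transform, and geometric means imply logs, so this is an ambiguity.
- A reader might think Phase 1 already answered the saline comparison. Protocol 2.1.6 describes no saline arm; the named controls are hepatitis B vaccine.
- Formulation choice rests chiefly on the challenge result, and Protocol 2.2.1 says no immune correlate is known.
- SAP 5.1 switches to non-parametric tests if normality fails. That could avoid the pooled-variance problem, but it does not name the missing contrast.
- On days 7 and 28, unsampled days would simply yield no row.

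**Conclusion.** The point holds as an undeclared inconsistency. The SAP keeps hypothesis 2 but specifies no Group 2 vs 1 or Group 3 vs 1 IgG contrast. The protocol's between-formulation analyses (the contrasts in item c, and items d and f) are absent from the SAP and not listed in Section 7. Neither model states its log transform. This should be corrected before unblinding; it affects a secondary immunogenicity hypothesis, not the primary endpoint.

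The absence of the contrast is a matter of text and needs no assumption. The 9% figure is conditional. It assumes a placebo SD near zero and equal vaccine-arm SDs, and it concerns a contrast the SAP does not yet contain. It should guide how the contrast is added and should not be read as the error rate of the present plan. The sampling-day mismatch is correct but minor.

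**What to change.** In SAP 5.7.4.2:
1. State that log IgG is analysed in both models, and how undetectable values enter the log.
2. Keep the comparisons with placebo.
3. Add Group 2 vs 1 and Group 3 vs 1 at Day 126, the time point of protocol item f, as geometric mean ratios with 95% CI. Add Group 3 vs 2 if the all-pairs Tukey comparison is retained. Name one multiplicity rule, for example Tukey, or Holm over the two contrasts with Group 1.
4. Estimate the variance for these contrasts from the three vaccine arms only, or use Welch.
5. Name the same contrasts in the MMRM.
6. Limit IgG change summaries to days with an antibody draw: no day 7, and day 28 only after dose 3 (Day 140).

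In SAP Section 7, list every protocol item that is dropped or altered.

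The cost is SAP wording and a little more programming, with no new samples. Intervals widen slightly. With equal variances the change is from a critical value of 2.015 to 2.035, about 1%. If placebo is truly flat it is 2.035/1.745, about 17%, which is the width needed to hold 5%.
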